The study will consist of patients with non-allergic irritant rhinitis (NAIR) as defined by history (symptoms of nasal congestion, rhinorrhea, nasal itching or sneezing upon exposure to nasal irritants) and positive optical rhinometer (Rhinolux™, Rhios GmbH, and Germany) response with intranasal challenge with capsaicin (17). Participants will be sought from volunteers and those presenting to the outpatient Otolaryngology clinic at the University of Texas Medical School at Houston. Patients included in the study will be between the ages of 18 and 70 with no history of sinonasal surgery, intranasal steroid use for more than 4 weeks, intranasal or systemic antihistamine for 3 days, intranasal or systemic decongestants for 3 days, chronic rhinosinusitis, inflammatory or granulomatous diseases, asthma, allergic rhinitis, immunocompromised state or radiation to the head and neck.

Allergy Testing to Identify and Exclude Subjects with Allergic Rhinitis

All previously consented subjects with history consistent with NAIR will be screened with a skin prick test (Multi-Test II Lincoln Diagnostics, Decatur, IL USA) to 6 common allergens including dust mite, mixed mold extract, cat hair, grass pollen, insect extracts, and bermuda grass extract to exclude allergic rhinitis. Those with confirmed negative skin prick testing will be eligible for the study.

Capsaicin Challenge and Optical Rhinometry

The optical rhinometer apparatus is applied to either side of the nasal dorsum according to the manufacturer's instructions. A one-minute baseline recording will be obtained and averaged. Capsaicin solution (Sigma Chemical, St. Louis, MO USA) will be diluted in 1% ethanol vv and 0.9% normal saline. 1% ethanol in 0.9% normal saline will serve as the vehicle solution. A mucosal atomizer device (MAdomizer, Wolfe Tory Medical, Inc Salt Lake City, UT USA delivering a 100 μ l solution will be used to deliver a dose of capsaicin totaling 1.5 μ g of capsaicin (0.05 mM) to the anterior face of the inferior turbinate of each nare. The maximum change in optical density (OD) will be recorded. Patients with a maximum change in OD of at least 0.2 will be considered a positive response and included in the study.

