A composite symptom score will be recorded based a commonly used rhinitis rating system as recommended by the FDA for clinical trial studies on allergic rhinitis (<http://www.fda.gov/downloads/Drugs/GuidanceComplianceRegulatoryInformation/Guidances/ucm071293.pdf>). Each of the following 4 symptoms: nasal itching/tingling, nasal congestion, sneezing and rhinorrhea, will be rated on a 0-3 scale of severity (Appendix B) and a summed composite score will be recorded for each subject.

Capsaicin Treatment Concentration

The capsaicin solution will be prepared by using the formula previously reported by Van Rijswijk et al; (0.1mmol/l) diluted in ethanol and 0.9% normal saline (19). Using the MAD, 0.8mL will be delivered to each nasal cavity for a total of 24.4 ug per nasal cavity.

Study Procedure:

[figure not shown]
There will be a total of 4 visits. On the first visit, patients will be consented and undergo skin prick testing, the capsaicin challenge and Optical Rhinometry. Prior to undergoing the capsaicin challenge, a composite symptom score will be recorded. Patients with confirmed negative skin prick testing, and positive response on ORM will be eligible for the study and will be asked to return for treatment. Those who are not eligible will not be responsible for any costs associated with screening and will be compensated for parking as well as \$25.00 for their time.

At the second visit, the NAIR patients will have been randomized and blinded into two groups: Group A will be treated with vehicle spray; and Group B will be treated with the capsaicin spray. The PI will be blinded to the treatment. A member of the research team, which consists of Drs. [name], [name], [name], and [name] (research coordinator), will assist during the randomization and distribution of appropriate pre-made medications so that the PI and subjects remain blinded.

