5 consecutive applications of capsaicin or placebo will be administered intranasally, with 1 hour between each application. Fifteen minutes prior to each application of medication, the nasal mucosa will be anesthetized with 100 ul of 1% lidocaine will be applied to each nasal cavity via MAD for all study participants. The lidocaine should not alter the nasal mucosa reaction to capsaicin; and is meant to anesthetize the area from the mild stinging of capsaicin. In fact, because lidocaine has a very mild stinging sensation at times; it can serve to mask the stinging one may get with intranasal capsaicin. Using the MAD, 100 μ L of 1% ethanol in 0.9% saline solution (Group A) or 0.8 mL solution with (0.1mmol/l) of capsaicin in 1% ethanol in 0.9% saline (Group B) will be delivered to each nasal cavity. On this day, they will not need to undergo optical rhinometry. Patients will fill out composite symptoms scores before and five minutes after 1st and 5th treatments. Patients who complete this portion of the experiment will receive \$50 dollars in compensation as well as parking.

Patients will then follow up 4 and 12 weeks after initiating treatment. At the 4 week and 12 week follow-up appointments, subjects will undergo capsaicin challenge followed by ORM and composite symptom score of nasal symptoms will be reported. Patients who complete both follow up visits will receive \$25 dollars in compensation as well as parking.

Study Protocol

Compensation:

In summary, patients that undergo the screening process and complete the skin prick testing and intranasal capsaicin challenge and ORM will be compensated \$25 as well as parking validation. Patients that undergo the treatment will be compensated \$50 plus parking for completing that day. Patients that complete the study and return 4 and 12 weeks post treatment, will be compensated \$25 plus parking.

Data and Safety Monitoring:

Previous studies have shown that the concentration of capsaicin that will be used is generally well tolerated.

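### The vehicle arm is dosed at 100 µL per nostril and the capsaicin arm at 0.8 mL, an 8-fold mismatch in volume and ethanol that can unblind the trial; the vehicle volume should be 0.8 mL

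*Combined protocol and SAP*

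**What the plan says.** The treatment instruction is in Study Procedure. Each nasal cavity is to receive "100 μ L of 1% ethanol in 0.9% saline solution (Group A) or 0.8 mL solution with (0.1mmol/l) of capsaicin", with the capsaicin also made up in 1% ethanol and 0.9% saline. There are five applications, one hour apart.

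The section Capsaicin Treatment Concentration repeats the active volume and adds a dose: "Using the MAD, 0.8mL will be delivered to each nasal cavity for a total of 24.4 ug per nasal cavity". It gives no vehicle volume.

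Two other volumes of 100 µL appear in the protocol. One is the diagnostic challenge in Capsaicin Challenge and Optical Rhinometry, where 100 µL at 0.05 mM is said to carry 1.5 µg of capsaicin; that section also states that "1% ethanol in 0.9% normal saline will serve as the vehicle solution". The other is the pre-treatment 15 minutes before every application, when "the nasal mucosa will be anesthetized with 100 ul of 1% lidocaine will be applied to each nasal cavity via MAD" in both arms.

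On blinding, a member of the research team "will assist during the randomization and distribution of appropriate pre-made medications so that the PI and subjects remain blinded". On outcomes at this visit, "Patients will fill out composite symptoms scores before and five minutes after 1st and 5th treatments", and for rhinometry, "On this day, they will not need to undergo optical rhinometry".

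**The concern.** A vehicle control should differ from the active treatment only in the active ingredient. Here the arms also differ in the amount of liquid and ethanol put into the nose. Because one volume is in microlitres and the other in millilitres, the mismatch is easy to overlook.

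Two things are at stake.

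- **Blinding.** A 0.1 mL fill and a 0.8 mL fill can be told apart by anyone who handles or watches them. The protocol does not say who gives the spray, how the devices are filled, or whether the principal investigator is absent. The Quality control and assurance paragraph has the principal investigator, who is meant to be blind, recording all the data sheets. Subjects could possibly be unblinded too, since each has the 100 µL lidocaine spray as a reference before every application.
- **Confounding.** Volume and ethanol load are inseparable from arm. The composite score includes congestion and rhinorrhea and is reported by the patient five minutes after the 1st and 5th treatments, when the extra liquid is most likely to matter. The Statistical Analysis section does not say which post-treatment scores enter the t-test, so these are not excluded.

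**Working it through.** **Inputs**

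- Vehicle: 100 µL per nasal cavity, 1% ethanol (Study Procedure).
- Capsaicin: 0.8 mL per nasal cavity, 0.1 mmol/L, 1% ethanol (Study Procedure); 24.4 µg per nasal cavity (Capsaicin Treatment Concentration).
- Challenge: 100 µL at 0.05 mM, 1.5 µg (Capsaicin Challenge and Optical Rhinometry).
- Five applications, two nasal cavities; lidocaine 100 µL per cavity before each application (Study Procedure).

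**Step 1: reproduce the stated dose.** Dose = concentration × volume × molar mass. The protocol gives no molar mass, so it is backed out of each dose statement:

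- Challenge: 1.5 µg / (0.05 mmol/L × 0.1 mL) = 300 g/mol. If 1.5 is rounded (1.45 to 1.55), the range is 290 to 310 g/mol.
- Treatment: 24.4 µg / (0.1 mmol/L × 0.8 mL) = 305 g/mol.

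The second value lies within the range of the first, so the two statements agree and 24.4 µg is reproduced with 0.8 mL.

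**Step 2: could both arms have been meant to receive 100 µL?** At 0.1 mmol/L and 0.1 mL, 290 to 310 g/mol gives 2.9 to 3.1 µg, not 24.4 µg. Matching the arms at 100 µL would contradict the stated dose. The only match that keeps the dose is 0.8 mL in both arms.

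**Step 3: size of the mismatch.** Volume ratio = 800 µL / 100 µL = 8. Both arms are stated at 1% ethanol, so the ethanol ratio is also 8. Ethanol = volume × 1%, taken as v/v.

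| Reading | Vehicle, both cavities | Capsaicin, both cavities | Ratio |
|---|---|---|---|
| Volumes per application, 5 applications | 5 × 2 × 0.1 = 1.0 mL; ethanol 10 µL | 5 × 2 × 0.8 = 8.0 mL; ethanol 80 µL | 8 |
| Volumes are day totals | 2 × 0.1 = 0.2 mL; ethanol 2 µL | 2 × 0.8 = 1.6 mL; ethanol 16 µL | 8 |
| Mixed: vehicle per application, capsaicin a day total | 5 × 2 × 0.1 = 1.0 mL; ethanol 10 µL | 2 × 0.8 = 1.6 mL; ethanol 16 µL | 1.6 |

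The first reading is the likeliest. The mixed one is strained, because a single sentence with one verb assigns both volumes.

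**Step 4: the reference spray.** Per application and nostril, treatment volume over lidocaine volume is 100/100 = 1 for vehicle and 800/100 = 8 for capsaicin.

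**Step 5: after correction.** With vehicle at 0.8 mL, each arm receives 0.8 mL and 8 µL of ethanol per nasal cavity per application, the ratio is 1, and the capsaicin dose stays at 24.4 µg.

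**The case against.** The strongest reply is that this is a typing slip with uncertain consequences. Six points deserve an answer.

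- The dose arithmetic confirms the capsaicin volume only; nothing in it contradicts 100 µL of vehicle. That is correct. The vehicle figure fails because a blinded vehicle control should match, and the arithmetic then shows which of the two volumes must move.
- Under the mixed reading the ratio falls to 1.6. This cannot be ruled out from the wording, but it still leaves the arms unequal.
- A figure under Study Procedure is not available in the text reviewed and might show volumes. That is possible. The written instruction would still need to agree with it.
- Each subject receives only one volume and is not said to know what the other arm gets. This stands: a subject may notice a large spray without being able to infer the arm, so subject unblinding is a possibility only.
- If the team member who distributes the medication also sprays it, the principal investigator need not see the volume. This is true, but the protocol does not say so.
- Capsaicin stings, and every enrolled subject has already felt it at the screening challenge. Equal volumes will not remove that cue, which the lidocaine is partly meant to mask. This stands as a limit on what the correction achieves. It gives no reason to leave a second, avoidable cue in place.

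**Conclusion.** The concern holds. As written, the control arm receives one eighth of the volume and ethanol of the active arm, which conflicts with a double-blind, vehicle-controlled comparison. The 8-fold ratio assumes that both volumes are read on the same basis, as the sentence naturally does.

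That the mismatch can unblind staff, and possibly subjects, is an inference from the volumes; the documents do not report it. Its effect on the five-minute symptom scores is direct in mechanism but cannot be sized. An effect on optical density at 4 and 12 weeks is only possible, since no rhinometry is done on the treatment day, and it cannot be sized either. The 100 µL may have been carried over from the challenge or the lidocaine volume. The documents do not settle that, nor whether any patient received unequal volumes.

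**What to change.** Amend the treatment sentence in Study Procedure so that Group A receives 0.8 mL of 1% ethanol in 0.9% saline per nasal cavity, in identical devices with the same fill and the same number of sprays as Group B. State whether 0.8 mL is per application. It would also help to state who gives the spray.

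If patients have already been treated, check what each arm received. If the volumes were unequal, report this with the results and qualify the description of the trial as double-blinded.

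The cost is one corrected sentence, the amendment that carries it, and identical filling of the devices. No extra patients, staff or procedures are needed.

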Regarding the lidocaine, it is administered routinely in our clinic prior to nasal endoscopy and flexible laryngoscopy exams. Side effects can include minor stinging and burning when applied to the nose. Because it is an intranasal spray, there is a risk that patients will swallow it and may have difficulty swallowing for up to 45 minutes after application. We express to patients that they should avoid eating or drinking anything up to 45 minutes after the lidocaine application.

Regarding skin prick testing, patients may have mild discomfort where the skin is pricked. They may have symptoms such as itching, a stuffy nose, red watery eyes, or a skin rash. Rarely, people can have anaphylaxis, but this usually only occurs with intradermal testing, which we will not be performing. If patients become short of breath, we do have oxygen available in the clinic.

Patients will be educated to call the outpatient Otolaryngology clinic at the University of Texas Medical School at Houston if there are any adverse effects.

Human Subjects:

Participants will be sought from those presenting to the outpatient Otolaryngology clinic at the University of Texas Medical School at Houston. Patients included in the study will be between the ages of 18 and 70 with no history of sinonasal surgery, intranasal steroid use for more than 4 weeks, intranasal or systemic antihistamine for 3 days, intranasal or systemic decongestants for 3 days, chronic rhinosinusitis, inflammatory or granulomatous diseases, asthma, allergic rhinitis, immunocompromised state or radiation to the head and neck.

This is a small study of only 22 subjects total and as addressed previously we anticipate screening 60 subjects in order to complete our enrollment. . Our practice consists of adult patients with a majority of who speak and read English. Therefore, it is unlikely to exclude a subject from the study because they do not speak or read English

Statistical Analysis:

Justification of sample size:

Using [name] paper (17) : his article showed the average maximum optical density in NAIR patients was 0.2 (SD 0.051), seen when using the 0.05 mM concentration of capsaicin during the capsaicin challenge and ORM. Healthy control subjects had a mean maximal OD change of 0.174 (SD 0.034). This was significant to $p=0.01$. Based on this data, 11 patients will need to be recruited to detect a significant post-treatment change.

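### The visible protocol describes only patient-initiated calls for reporting adverse effects and lists no enquiry at the treatment visit or at weeks 4 and 12, so harms are likely to be under-recorded

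*Combined protocol and SAP*

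**What the plan says.** The Data and Safety Monitoring section opens with earlier evidence: "Previous studies have shown that the concentration of capsaicin that will be used is generally well tolerated". It goes on to effects expected from lidocaine (stinging, burning, difficulty swallowing) and from skin testing. Its one instruction on reporting is: "Patients will be educated to call the outpatient Otolaryngology clinic" should adverse effects occur.

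The Study Procedure section sets the contacts. "There will be a total of 4 visits": screening, treatment, week 4 and week 12. On the treatment day, "5 consecutive applications of capsaicin or placebo will be administered intranasally, with 1 hour between each application". The record listed for that day is: "Patients will fill out composite symptoms scores before and five minutes after 1st and 5th treatments". Afterwards, "Patients will then follow up 4 and 12 weeks after initiating treatment", and at those two visits "subjects will undergo capsaicin challenge followed by ORM and composite symptom score of nasal symptoms will be reported".

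The composite score, defined under Capsaicin Challenge and Optical Rhinometry, grades four nasal symptoms from 0 to 3: itching or tingling, congestion, sneezing and rhinorrhea. The Statistical Analysis section covers the symptom score, optical density and the correlation between them. It has no tabulation of adverse events. Data Handling and Record Keeping refers to a data sheet that is not reproduced.

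**The concern.** Waiting for a patient to call is passive reporting, and mild or short-lived effects are the ones most easily lost. The plan itself expects effects of that kind: Study Procedure mentions mild stinging from capsaicin, and Data and Safety Monitoring adds stinging, burning and temporary swallowing difficulty from lidocaine. Most would arise on the treatment day, while the patient is at the clinic and has no reason to phone. The form completed that day has no place for them.

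Reporting could also differ by arm. Study Procedure gives different volumes for the vehicle and capsaicin sprays and acknowledges that capsaicin stings. Patients who guess their arm may be more or less inclined to call. Asking everyone the same question reduces that risk.

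At stake is how the harm record can be read at the end. With 11 patients per arm, one or two missed events can turn a few reports into none.

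**Working it through.** The plan states no figure for adverse events, so there is nothing to reproduce. The check has two parts.

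**What is listed at each visit**

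Four visits less the screening visit leave 3 contacts at which harms could be asked about.

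| Visit | Procedures listed | Adverse-event enquiry listed |
|---|---|---|
| Treatment day | Lidocaine and study spray, 5 times; symptom score before and 5 minutes after applications 1 and 5 | None |
| Week 4 | Capsaicin challenge, optical rhinometry, symptom score | None |
| Week 12 | Capsaicin challenge, optical rhinometry, symptom score | None |

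Five applications an hour apart span 4 × 1 = 4 hours, so patients are at the visit for at least 4 hours. No score is listed around applications 2 to 4.

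**Illustration of size**

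Inputs:
- n = 11 per arm, from the sample size statement.
- p, the true proportion of capsaicin patients with an event: not in the documents; assumed 20-30%.
- q, the probability that an affected patient calls: not in the documents; assumed 30-50%.

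Treating patients as independent, the chance that an arm records no events is (1 − p × q)^11. With full ascertainment, q = 1.

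| p | q = 0.3 | q = 0.5 | q = 1 |
|---|---|---|---|
| 0.2 | 0.94^11 = 51% | 0.90^11 = 31% | 0.80^11 = 8.6% |
| 0.3 | 0.91^11 = 35% | 0.85^11 = 17% | 0.70^11 = 2.0% |

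The expected number of affected patients is 11 × p = 2.2 to 3.3. The expected number recorded through calls is 11 × p × q, from 11 × 0.2 × 0.3 = 0.66 to 11 × 0.3 × 0.5 = 1.65.

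The result moves with the inputs. At p = 0.2 and q = 0.25 the chance of none is 0.95^11 = 57%. At p = q = 0.5 it is 0.75^11 = 4.2%.

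**What a clean record could show at best**

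With every patient asked and 0 of 11 affected, the exact one-sided 95% upper limit is 1 − 0.05^(1/11) = 23.8%. The two-sided 95% interval runs up to 1 − 0.025^(1/11) = 28.5%.

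**The case against.** The strongest reply is that the call-in sentence is an instruction to patients, naturally read as covering time away from the clinic. It does not say that calls are the only route or that staff will not ask. The data sheet, the procedure figure and the appendix with the rating scale are not visible, and an adverse-event field could sit on the data sheet. This stands, and it limits the point to what the visible protocol describes.

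The symptom score also gives some systematic capture. It is completed by every treated patient, and sneezing, itching and rhinorrhea are among the irritative effects that the Background section describes. That stands in part: the score overlaps with local irritation, but it is used for efficacy and omits other effects the plan expects. Swallowing difficulty is attributed to lidocaine, which both arms receive, so it would say little about capsaicin as such.

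The illustration rests on assumed rates and applies the calling probability even to events at the visit, which a patient might simply mention. That also stands.

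A reader might infer two stronger things that the documents do not support. One is that call-in reporting delays the team's awareness on the treatment day. Patients are then at a study visit receiving repeated applications, and nothing suggests they must phone to be noticed. The other is that the trial plans to conclude that capsaicin is well tolerated. That statement concerns previous studies; the Objectives contain no safety aim and no safety analysis is planned.

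**Conclusion.** The point holds in a limited form. Patient calls are the only reporting route the visible protocol describes. No enquiry is listed at any of the three visits after screening, and the score taken there does not cover stinging, burning, pain or swallowing difficulty. Harms are therefore likely to be under-recorded, unless the data sheet already has a field for them.

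The direction is an inference from the passive method, and the documents do not allow its size to be estimated. The 17-51% chance of no recorded events, against 2-9% with full ascertainment, is an illustration conditional on the assumed rates. A sparse record obtained this way could not be read as evidence of tolerability. Even a fully ascertained 0 of 11 would leave event rates of up to about 24% open (one-sided 95%).

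This is a worthwhile, inexpensive improvement. It does not touch the efficacy comparisons.

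**What to change.** First check the data sheet. If it already carries an adverse-event field completed at each visit, one sentence in Data and Safety Monitoring saying so closes the collection part of the point.

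Otherwise keep the call-in instruction and add text along these lines: at a fixed point during the treatment visit, and at weeks 4 and 12, the blinded principal investigator asks every patient in both arms the same adverse-event question and records the answer on the data sheet; events reported by phone are added to the same record.

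In Statistical Analysis, add one table giving the number of patients with any adverse event by arm, with exact 95% intervals, and a sentence stating that 0 of 11 would exclude only rates above about 24% (one-sided 95%).

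No new visit or staff is needed: Study Procedure already blinds the principal investigator, and Quality control and assurance already has that role recording the data sheets. The cost is a few data sheet lines, one table and a few minutes per visit. The recorded event count will probably be higher, because more of what happens is being recorded.

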**Double-Blinded Randomized Prospective Trial of Intranasal Capsaicin Treatment for Non-
Allergic Irritant Rhinitis**

NCT02493257

Version Date: 11/18/2019

IRB NUMBER: HSC-MS-14-0173
IRB APPROVAL DATE: 11/18/2019

Protocol Title: Double-Blinded Randomized Prospective Trial of Intranasal Capsaicin Treatment for Non-Allergic Irritant Rhinitis

Principal Investigator: [name]

Co-Investigators: [name] PhD; [name]; [name]

Study Coordinator: [name] PhD

Population: The study population will consist of patients with non-allergic irritant rhinitis (NAIR) as defined by history (symptoms of nasal congestion, rhinorrhea, nasal itching or sneezing upon exposure to nasal irritants) and positive optical rhinometer (Rhinolux™, Rhios GmbH, and Germany) response with intranasal challenge with capsaicin. Participants will be sought from those presenting to the outpatient Otolaryngology clinic at the University of Texas Medical School at Houston. Patients included in the study will be between the ages of 18 and 70 with no history of sinonal surgery, intranasal steroid use for more than 4 weeks, intranasal or systemic antihistamine for 3 days, intranasal or systemic decongestants for 3 days, chronic rhinosinusitis, inflammatory or granulomatous diseases, asthma, allergic rhinitis, immunocompromised state or radiation to the head and neck.

Sample size: 11 participants will need to be recruited to each group (experimental and control) to detect a significant post-treatment change. In order to reach our target enrollment of 22 participants we expect to screen 60 subjects.

Number of sites: single site

Study duration: 13 weeks

Subject duration: 13 weeks

General Information: The proposed study seeks to investigate the effect of intranasal capsaicin treatment in patient with Non-allergic irritant rhinitis (NAIR), as well as evaluate optical rhinometry (ORM) as a means to quantify symptomatic improvement in NAIR patients during and after treatment.

Background Information:

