Currently, intranasal steroids are the only FDA approved agents used in NAIR. Topical applications of capsaicin have been used in the treatment of pain particularly in post-herpetic neuralgia, post mastectomy pain, and hypersensitivity disorders of the lower urinary tract (7-9). LaCroix et al has shown that repeated administration of intranasal capsaicin decreased nasal symptoms in NAIR patients (10). Although multiple studies using intranasal capsaicin have been shown to improve nasal symptoms of NAIR patients (11-13); there have been no studies in which NAIR patients were objectively identified and symptom improvement was objectively monitored.

Optical rhinometry (ORM) has been proposed to be a useful instrument in the assessment of nasal blood flow, as an indirect measurement of nasal congestion (14). A positive correlation has been made between optical rhinometry and symptom scores for nasal congestion in nasal provocation testing (15). ORM has also been shown to correlate with changes in nasal cavity cross sectional area measured via acoustic rhinometry (16). In addition, our group recently reported that ORM following 0.05 mM capsaicin challenge can be utilized to identify NAIR patients (17).

A study by Lambert et. al. (2012) was able to objectively identify patients with NAIR by intranasal capsaicin challenge followed by assessment with optical rhinometry (17). Studies have shown that capsaicin therapy can improve symptoms of patients historically identified with NAIR via visual analog scale (VAS) rating of symptoms and symptom surveys; however, there has been no study evaluating the capsaicin therapy on patients objectively identified as NAIR patients.

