Student's t-test will be used to compare the mean change in composite symptom scores pre and post-treatment in both groups. Student's t-test will also be used to compare changes in maximal optical density in response to capsaicin challenge pre- and post-treatment in both

groups. Statistical significance will result if $p < 0.05$. The Spearman Rank Correlation will be used to analyze associations between composite symptom scores and changes in OD.

Ethics:

IRB approval will be sought from CPHS

Data Handling and Record Keeping: In order to maintain confidentiality, a data sheet with patient's names and data collected for the study (see data sheet) will be stored in a locked file cabinet within the department of Otorhinolaryngology. Access to data sheets in patient will be limited to co-investigators and research coordinator. Only de-identified data or collective data will be shared.

Quality control and assurance: In order to confirm that the diagnosis of non-allergic irritant rhinitis is accurate and made in an unbiased manner, a history of rhinitic symptoms will be confirmed with objective skin testing.

All datasheets will be recorded by PI and reviewed by at least one of the other 3 co-investigators to ensure accuracy in the recording of clinical data.

Publication Plan: This study has been funded by the American Association of Otolaryngic Allergy (AAOA) Foundation Grant. Results from this study will be presented at a future AAOA national meeting and initial publication rights will be given to the International Forum of Allergy and Rhinology.

All enrolled subjects will be notified of any publication resulting from this study, but these publications will present data on only the aggregate group.

REFERENCES

2. Hummel T. Assessment of intranasal trigeminal function. *Int J Psychophysiol*. 2000 May;36(2):147-55.

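### The 11 patients per group said to follow from the cited optical density data cannot be reproduced from the printed figures, and no inputs are given for the planned test of change

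*Combined protocol and SAP*

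**What the plan says.** Under Statistical Analysis, Justification of sample size, the plan takes its inputs from a cited capsaicin challenge study. For patients, "the average maximum optical density in NAIR patients was 0.2 (SD 0.051"; for comparison, "Healthy control subjects had a mean maximal OD change of 0.174 (SD 0.034". It adds that the cited difference had p=0.01, and then concludes: "Based on this data, 11 patients will need to be recruited to detect a significant post-treatment change".

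The Sample size entry at the front supplies the unit: "11 participants will need to be recruited to each group (experimental and control) to detect a significant post-treatment change". The total is 22, and 60 are expected to be screened.

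The analysis these numbers should support is described just after the justification. Student's t-test will "compare changes in maximal optical density in response to capsaicin challenge pre- and post-treatment" in both groups, with significance at p < 0.05. The same measure also decides entry (Capsaicin Challenge and Optical Rhinometry): "Patients with a maximum change in OD of at least 0.2 will be considered a positive response and included in the study".

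No power, sidedness, target change, SD of change or pre/post correlation is given anywhere. The background states only a qualitative expectation, that the positive challenge response will disappear after treatment.

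**The concern.** The justification presents 11 as a consequence of four printed numbers, so a reader should be able to get from those numbers to 11 with an ordinary formula. Two things stand in the way.

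- **The arithmetic.** A difference of 0.026 against SDs of 0.051 and 0.034 is a moderate standardised effect, and 11 per group is far below what such an effect usually requires.
- **The quantity.** Patients versus healthy people at one time point is not a change after treatment, nor a difference in change between capsaicin and vehicle.

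This is the only justification for the size of the trial, and evaluating treatment response by optical rhinometry is the first listed objective. If the basis for 11 is unknown, nobody can say what OD effect 22 patients can detect, and a non-significant OD result could be misread as no effect.

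**Working it through.** **Inputs from the plan.** NAIR mean 0.2, SD 0.051; healthy mean 0.174, SD 0.034 (Justification of sample size). Significance level 0.05 (Statistical Analysis). 11 per group (Sample size entry).

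**Assumptions, because the plan is silent.** Two-sided test, with one-sided also tried; 80% power as the benchmark. Results use the noncentral t distribution unless marked as a normal approximation.

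**Step 1: standardised effect.**
- Difference = 0.2 − 0.174 = 0.026
- Pooled SD = √((0.051² + 0.034²)/2) = √0.0018785 = 0.0433
- d = 0.026/0.0433 = 0.60

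**Step 2: attempt to reproduce 11 with a two-sample test.** By normal approximation, n per group = 2(1.960 + 0.842)²/0.60² = 43.6, so 44. The t-test gives 44.6, so 45. At 90% power the t-test needs 60.

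Per-group n for 80% power by t-test, for each choice of SD:

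| SD used | d | two-sided | one-sided |
|---|---|---|---|
| 0.051 | 0.51 | 62 | 49 |
| pooled 0.0433 | 0.60 | 45 | 36 |
| 0.034 | 0.76 | 28 | 22 |

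The range is 22 to 62. None is near 11.

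**Step 3: power of 11 per group for the printed contrast (pooled SD).** 26.8% two-sided; 38.8% one-sided.

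**Step 4: look for any route to 11.** Use a one-sample normal approximation, one-sided, at 80% power, with the healthy SD of 0.034 standing in for the SD of change:
- n = ((1.645 + 0.842) × 0.034/0.026)² = 10.6, so 11
- The corresponding t-test gives just over 12, so 13

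Other one-sample t-tests that use a printed SD as the SD of change need up to 33. The plan states none of these choices.

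**Step 5: what the planned test of change would need.** Suppose 0.026 were the target change; the plan does not say that it is. At 11 per group, two-sided 0.05 and 80% power, the detectable standardised effect is 1.256 between arms and 0.938 for a paired test within one arm. The SD of change could then be at most:
- between arms: 0.026/1.256 = 0.0207
- within an arm: 0.026/0.938 = 0.0277

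The plan gives no SD of change to set against either limit.

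**Step 6: the entry cut-off.** Only patients with an OD change of at least 0.2 are admitted, and 0.2 is also the printed NAIR mean. If OD in such patients were normal with mean 0.2 and SD 0.051 (an assumption), those above the cut-off would have:
- mean 0.2 + 0.051 × √(2/π) = 0.241
- SD 0.051 × √(1 − 2/π) = 0.031

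Enrolled baselines will therefore not follow 0.2 (SD 0.051), so neither the printed mean nor the printed SD carries over to the trial population.

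**The case against.** The strongest reply is that the plan states no power, so strictly its inputs fix no sample size and cannot contradict 11. Routes to 11 exist: the one-sample, one-sided approximation in Step 4, or a paired within-arm test whose SD of change is no more than 0.0277. The justification speaks of a post-treatment change, and the analysis wording does not exclude a within-arm reading. This stands, and it limits the claim to non-reproducibility. It does not rescue the plan's sentence, because those choices are not stated and a within-arm test does not compare the randomised groups.

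The cut-off also weakens any claim about true power. With enrolled baselines near 0.241, a fall to 0.174 would be about 0.067, well above 0.026. Part of that fall would be regression to the mean in both arms, so it does not show that 11 is enough. It does show that 0.026 should not be taken as the expected treatment effect.

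A reader might go further and infer a misprint, since the NAIR mean has one decimal and the other figures three. The documents do not support choosing a value. With the other figures unchanged, a NAIR mean of 0.23 gives 11 per group by t-test; so does a healthy mean of 0.147 by normal approximation (12 by t-test). The source's group sizes are not given, so p=0.01 cannot decide. Nor does a mean equal to the cut-off show an error: about half of NAIR patients testing positive is compatible with screening 60 to enrol 22 (37%), since skin-prick exclusions also apply. All this supports is checking the figures.

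**Conclusion.** The concern holds as a failure of derivation. From the printed figures, a two-sided two-sample t-test at 0.05 gives about 27% power at 11 per group (39% one-sided). It needs about 45 per group for 80% power, with 22 to 62 across the variants tried. The 80% benchmark and the form of the test are assumptions, because the plan gives neither.

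A reader might infer that 11 per group is too few, or that the trial has 27% power for its treatment effect. Neither follows. The 27% applies to a 0.026 difference between two groups with the cited SDs. The treatment effect, the SD of change and the enrolled baseline distribution are unknown. What is established is that the stated data do not yield 11 by a conventional calculation, and that nothing in the plan sizes the trial for the test of change it intends to run. The sentence should be corrected before the sample size is relied on.

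**What to change.** 1. Check all four means and SDs in the justification against the cited source, to the precision reported there, and correct any misprint.
2. Replace the concluding sentence of the justification, and the matching sentence in the Sample size entry, with the actual basis: the between-arm difference in change in maximal OD, sidedness, target difference, SD of change in patients who meet the entry cut-off, and resulting power. If no such basis exists, say that 22 was not set by a power calculation. In that case, if the printed figures stand, add that 11 per group has about 27% power (two-sided 0.05) for a 0.026 difference between two groups with those SDs.
3. Report the between-arm difference in OD change with its 95% CI, and do not read a non-significant result as absence of effect.

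Cost: one check of the source, edits to two sample-size passages, and one reporting rule. No patients, visits or measurements are added. The downside is that the stated justification becomes less favourable.
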